### **Secondary outcomes (assessed 48 hours after randomization or as indicated)**

- Per amendment after first interim analysis Nov 5, 2020, we added two secondary outcomes:
- PaO2/FiO2 improvement from pre-to-post intervention at 24 hours post randomization.
- Amendment Nov 5, 2020: add the outcome "Decrease in ventilatory dead space as estimated by the ventilatory ratio at 48 hours." Based on a recent study, (Orfanos S, El Hussein I, Nahass T, et al. Observational study of the use of recombinant tissue-type plasminogen activator in COVID-19 shows a decrease in physiological dead space. ERJ Open Res 2020; 6: 00455-2020), this outcome seems to appropriate to assess the efficacy of the intervention. As most of the subjects do not have capnography data, we will be using the ventilatory ratio, which has been shown to correlate well with dead space.
- Achievement of PaO2/FiO2 ≥ 200 or 50% increase in PaO2/FiO2 (whatever is lower)
- National Early Warning Score (NEWS2): based on 7 clinical variables (respiration rate, oxygen saturation, any supplemental oxygen, temperature, systolic blood pressure, heart rate, level of consciousness).
- NIAID ordinal scale: The ordinal scale is an assessment of the clinical status as follows: 1) Death; 2) Hospitalized, on invasive mechanical ventilation or extracorporeal membrane oxygenation (ECMO); 3) Hospitalized, on non-invasive ventilation or high flow oxygen devices; 4) Hospitalized, requiring supplemental oxygen; 5) Hospitalized, not requiring supplemental oxygen - requiring ongoing medical care (COVID-19 related or otherwise); 6) Hospitalized, not requiring supplemental oxygen - no longer requires ongoing medical care; 7) Not hospitalized, limitation on activities and/or requiring home oxygen; 8) Not hospitalized, no limitations on activities. (combined items 7 and 8 as our study is limited to hospital)
- 48 hour in-hospital mortality

- 14 days in-hospital mortality
- 28 days in-hospital mortality
- ICU-free days (up to 28 days)
- In-hospital Coagulation-related event-free (arterial and venous) days (up to 28 days)
- Ventilator-free days (up to 28 days)
- Successful extubation (no re-intubation for >3 days after initial extubation)
- Successful weaning from paralysis for > 3 days after initial termination
- Survival to discharge

### Section 3: Study Methods

**3.1. Trial design** Multicenter, pragmatic, randomized, open label, rapidly adaptive, controlled, clinical trial

The trial has a novel design with modified stepped-wedge and adaptive features in order to rapidly identify the intervention group with the highest chance of benefit. This unconventional design is appropriate for the current circumstances of the pandemic caused by a new, lethal and morbid virus infection (COVID-19) for which no known treatment exists. The below figure illustrates the design. In brief, the patients will be sequentially assigned to one of three following groups:

[figure not shown]
[figure not shown]
- Group tPA50 will receive 50 mg of tPA intravenous bolus administration over 2 hours, given as a 10 mg push followed by the remaining 40 mgs over a total time of 2 hrs (not to exceed 0.9mg/kg dose). Immediately following the tPA infusion, 5000 U of UFH will be delivered and the heparin drip will be continued to maintain the activated partial thromboplastin time at 60-80sec (2.0 to 2.5 times the upper limit of normal). This tPA protocol is a modification of the GUSTO I to III trials. 44,45
- Group tPA50 plus drip will receive 50 mg of tPA intravenous bolus administration over 2 hours, given as a 10 mg push followed by the remaining 40 mgs over a total time of 2 hrs (not to exceed 0.9mg/kg dose). Immediately following this initial tPA infusion, we will initiate a drip of 2 mg/hr tPA over the ensuing 24 hours (total 48 mg infusion) accompanied by an infusion of 500 U/hr heparin during the tPA drip. After this, heparin dose will be increased slowly to maintain a PTT between 60 and 80 sec, titrated per attending's discretion.
- Control: institution's protocol for ARDS

In order to rapidly accrue patients in one intervention group with a concurrent control, the first 10 patients will be randomly assigned to Group tPA50 or Control (Standard-of-care) when the first interim analysis occurs. If no stopping criteria are met, the next 10 patients are randomly

assigned to Group tPA50 or Control when the second interim analysis is done. If no criteria for stopping or dropping an arm are met, the next 10 patients are randomly assigned to Group tPA50 plus drip or Control when the third interim analysis is done. Finally, if no criteria for stopping or dropping an arm are met, the trial progresses with patients being randomized to Group tPA50 plus drip or Control up to the final analysis at n=50.

## INITIAL DESIGN ANALYSIS

## NEW DESIGN AFTER 1st INTERIM

**Proposed amendment 11/5/2020:** Per the adaptive plan above, changes in dose and mode of administration of tPA were pre-planned. Based on the first interim analysis and feedback from our DSMB, we propose to change the study arm in the second deployment of the intervention to the same dose and mode of administration of the first phase (i.e. 50mg bolus dose, with a second dose if necessary as prescribed above).

**Assuming NO stopping criteria (as described in the protocol) are met, we will proceed as follows:**

- 1) If at the end of the second intervention deployment (total of 20 patients randomized), the primary outcome (PaO2/FiO2 ratio at 48 hours) improves by  $\geq 50\%$ , the study group will continue to receive the dose of the first phase (i.e. 50mg bolus dose, with a second dose if necessary as prescribed above) till the end of the study (total of 50 randomized patients). Interim analyses will be conducted as planned above, and submitted expeditiously to the DSMB, IRB and FDA for approval, yet enrollment will continue while these agencies deliberate and their feedback is received.
- 2) If at the end of the second intervention deployment (total of 20 patients randomized), the primary outcome improves (PaO2/FiO2 ratio at 48 hours) by  $\geq 20\%$ , or the secondary outcomes PaO2/FiO2 ratio at 24 hours improves  $\geq 20\%$ , or dead space decreases by 15%, or ICU- or ventilator-free days continue to exhibit a positive response (at least 2 days difference), we will modify the mode of administration of the second dose of tPA as follows: following the 50mg tPA bolus, we will initiate a drip of 2 mg/hr tPA over the

ensuing 24 hours (total 48 mg infusion) accompanied by an infusion of 500 U/hr heparin during the tPA drip. After this, heparin dose will be increased slowly to maintain a PTT between 60 and 80 sec, titrated per attending's discretion. Interim analyses will be conducted as planned above, and submitted expeditiously to the DSMB, IRB and FDA for approval, yet enrollment will continue while these agencies deliberate and their feedback is received.

### 3.2. Randomization details

Randomization is performed by the leading institution ([name] Shock Trauma Center at Denver Health, DH) using Research Randomizer  and automated via REDCap. All randomizations are conducted intra-hospital (i.e., no cluster randomization), to avoid the confounding effect of practice variation. Randomization is conducted in blocks of 10 to allow better distribution between groups at each interim analysis.

Each center will identify potentially eligible patients, obtain their consent, and enter in/exclusion criteria into the web-based REDCap instrument; if the patient is indeed eligible, the random assignment will be revealed to the institution's pharmacy, which will then release the drug at the appropriate dose (in case the patient is assigned to one of the intervention groups) or no drug will be released if the patient is randomized to the control group. This is defined as TIME ZERO.

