studies by Hardaway et al evaluating fibrinolytic therapy for treatment of ARDS used urokinase and streptokinase, the more contemporary approach to thrombolytic therapy involves the use of tissue-type plasminogen activator (tPA) due to higher efficacy of clot lysis with comparable bleeding risk to the other fibrinolytic agents.

Hypothesis:

We hypothesize that administration of tPA to patients with COVID-19 associated severe ARDS will improve pulmonary gas exchange and oxygenation via a decrease in pulmonary vascular microthrombi.

Study Design:

This is a Phase IIa clinical trial, open label, with a modified stepped-wedge design, testing systemic administration of fibrinolytic therapy with alteplase (tPA) versus standard of care for patients infected with COVID-19 resulting in severe respiratory failure. The design is a rapidly adaptive, pragmatic clinical trial, with 3 interim analyses and 1 final look at the data. Pre-planned adaptations described below will be contemplated at each interim analysis or earlier if recommended by the Data Safety Monitoring Board (DSMB).

Inclusion Criteria: We will include adult patients ages 18-75 years old with known or suspected COVID-19 infection with a PaO₂/FiO₂ ratio < 150 or inferred PaO₂/FiO₂ ratio from SpO₂ if ABG is unavailable (Table) persisting for > 4 hours despite optimal mechanical ventilation management according to each institution's ventilation protocols, and a neurological exam without focal signs or new deficits at time of enrollment (if patient is on paralytics, patient has been aroused sufficiently to allow a neurological examination to exclude new focal deficits or has MRI/CT scan in the last 4.5 hours with no evidence of stroke. Finally, patients must be on the ventilator for ≤10 days to be eligible. Based on experience with critically ill patients, longer ventilation time may be associated with increased risk of bleeding. Patients will be enrolled based on clinical features, without consideration of language (using hospital interpreters and translated consent), race/ethnicity, or gender. A neurological exam or CT/MRI scan to demonstrate no evidence of an acute stroke is needed due to a recent case-report of large-vessel stroke as a presenting feature of COVID-19 in young individuals.⁴⁴

SPO2	FIO2														
	0.3	0.35	0.4	0.45	0.5	0.55	0.6	0.65	0.7	0.75	0.8	0.85	0.9	0.95	1
80%	148	127	111	98	89	81	74	68	63	59	55	52	49	47	44
81%	151	129	113	101	91	82	76	70	65	60	57	53	50	48	45

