- 5) the bolus/infusion regimen was employed in the seminal 2001, Hardaway study⁷ demonstrating an improvement in oxygenation in patients with advanced ARDS,

6) the 2mg/ml tPA and 500 U heparin is the standard combination employed by interventional radiology for directed fibrinolysis (personal communication [name], Director of IR, UCSD), and

7) we are reticent to increase the tPA dose to 100 mg considering overall risk: benefit.

The above modification was predicted in the original COMIRB submission, in which we anticipated both dose and mode of administration changes is our adaptive plan.

The rationale and change to a bolus/infusion regimen was discussed with the DSMB, and they concurred without reservation (see letter from DSMB, in which they concur with proposed plan).

[figure not shown]
Design:

This is a multicenter ([name] Shock Trauma Center at Denver Health Medical Center (DHMC), University of Colorado Hospital (UCH), National Jewish Health / St. Joseph Hospital (NJH/SJH), Beth Israel Deaconess Medical Center (BIDMC), Long Island Jewish Hospital / North Shore University Hospital (LIJH/NSUH), Scripps Health (SH), St. Mary's Medical Center (SM), University of Miami (UM), Ben-Taub General Hospital (BT) and Dallas Methodist (DM)) Phase IIa clinical trial. The design is a pragmatic, open label, randomized, controlled, rapidly adaptive clinical trial, with 3 interim analyses and 1 final look at the data. For rapid efficacy assessment to isolate the arm(s) with the highest likelihood of success and lowest bleeding risk, we will deploy each intervention arm sequentially up to each interim analysis, in a modified stepped-wedge fashion, with pre-planned adaptations (below) at each interim analysis. Pre-planned adaptations described below will be contemplated at each interim analysis or earlier if recommended by the Data Safety Monitoring Board (DSMB).

[figure not shown]

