All randomizations are conducted intra-hospital (i.e., no cluster randomization), to avoid the confounding effect of practice variation. Randomization will be conducted in blocks of 10 to allow better distribution between groups at each interim analysis. It will be done by the Data Coordinating Center (DCC) and automated in an web-based REDCap data collection instrument. Upon confirmed eligibility and consent, the REDCap will reveal the group assignment to institution's pharmacy, which will then release the drug if the patient is assigned to the intervention group (Group tPA50, Group tPA50+drip). Time zero is assigned as the time of randomization. We anticipate that each of the five centers will enroll 8-12 patients.

The figure below illustrates the initial planned sequential, stepped-wedge design and the proposed new design after the adaptations driven by the first interim analysis. Study will continue during the interim analyses, unless a safety issue occurs.

INITIAL DESIGN

NEW DESIGN AFTER 1st INTERIM ANALYSIS

Re-bolusing of tPA, at the same dose, is permitted in the tPA50 intervention group in those patients who show an initial transient response (>20% improvement of PaO₂/FiO₂ over pre-infusion of alteplase at any of the measurements at 2, 6, 12 or 18 hours, but <50% improvement of PaO₂/FiO₂ at 24 hours after randomization); the repeat dose will be given between 24 and 36 hours after the initial tPA administration.

The same EXCLUSION criteria apply to the second tPA (alteplase) bolus. The heparin drip should be stopped two hours before the second tPA (alteplase) and re-started after the second alteplase infusion ends, at the same dose as before the second alteplase.

Other modifications of the dosing are as follows:

- Fibrinogen monitoring:** For all tPA administration groups, fibrinogen levels will be measured before and after tPA IV bolus, 6 hours after the start of the infusion, then every 6 hours for first 24 hours, and once a day for 6 days following treatment intervention in all the groups (see detailed lab testing schedule below). **If fibrinogen levels fall below 300 mg/dL, the second bolus of tPA (alteplase) is NOT indicated.**

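### The published fixed block of 10 in an open-label trial, with block level and list holder unclear, makes assignments partly predictable to anyone holding the block tally

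*SAP*

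**What the plan says.** SAP 3.2 (Randomization details) fixes one block size: "Randomization is conducted in blocks of 10 to allow better distribution between groups at each interim analysis". The Protocol's Design section repeats it: "Randomization will be conducted in blocks of 10 to allow better distribution between groups at each interim analysis". Treatment is not masked: "This is a Phase IIa clinical trial, open label, with a modified stepped-wedge design".

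Two matters are left open.

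- **Level of the blocks.** SAP 3.2 says: "All randomizations are conducted intra-hospital (i.e., no cluster randomization), to avoid the confounding effect of practice variation". This can mean separate blocks in each hospital, or only that patients rather than hospitals are randomised. SAP 3.1 counts patients across the trial ("the first 10 patients will be randomly assigned to Group tPA50 or Control (Standard-of-care) when the first interim analysis occurs"), then two further stages of 10 and a last stage up to 50. That favours trial-wide blocks without settling the question.
- **Who makes the list.** The SAP says: "Randomization is performed by the leading institution". The Protocol's Design section lists that hospital among the participating centres. The Protocol says of randomisation: "It will be done by the Data Coordinating Center (DCC) and automated in an web-based REDCap data collection instrument". Neither document says who may see the list or the running tally across sites.

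Both documents have REDCap disclose an assignment to the site's pharmacy only after eligibility and consent are complete.

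**The concern.** Release through REDCap hides the next entry in the table. It does not stop inference from past assignments, which are visible in an open-label trial, combined with a known block length. Once five patients in a 5:5 block share an arm, the rest of that block is determined.

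Entry leaves room to act on a guess. Ventilation must be optimal (Protocol) or maximal (SAP 5.2) for more than 4 hours, a patient on paralytics may have to be aroused for a neurological examination, and consent can be timed. Someone expecting control could delay a patient or put forward a sicker or healthier one. The primary outcome is change in PaO2/FiO2, so such selection could enter the treatment difference directly. SAP 6.3 and 6.4 plan inverse probability weighting on recorded covariates, which cannot correct selection on unrecorded judgement.

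**Working it through.** **1. The plan's own figure.** Inputs from SAP 3.2 (Sample size): SD 100, baseline mean 149, 25 v 25, design effect 1.12, about 20% inflation for death, final boundary 2.39658, power 80%. Effective n per arm = 25/1.2/1.12 = 18.6. Detectable difference = (2.39658 + 0.8416) × 100 × √(2/18.6) = 106 points, or 71% of 149. This reproduces the stated figure of more than 70% (0.70 × 149 = 104 points). The documents give no figure for predictability.

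**2. Predictability with the full block tally.** The ratio within a block is not stated in the readable text; 5:5 is inferred from 25 v 25. The guesser always names the arm that is behind. With m = 5:

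- expected correct guesses = m + 4^m/(2·C(2m,m)) − 1/2 = 5 + 1024/504 − 0.5 = 6.53 of 10 (65.3%, against 50% by chance);
- expected certain assignments = 2m/(m+1) = 10/6 = 1.67 of 10, or 8.3 of 50. The 10th is always certain, the 9th with probability 0.44, the 8th 0.17, the 7th 0.05 and the 6th 0.01.

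**3. Who holds that information.** SAP 3.2 expects five centres with 8-12 patients each. The Protocol's Design section lists ten centres or centre pairs, about 5 patients each. Both were simulated with N = 50.

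| Reading | Correct guesses | Certain | Bias per unit eta |
|---|---|---|---|
| Full tally, trial-wide blocks | 65% | 16.7% | 0.61 |
| Own patients only, trial-wide blocks, 5 sites | 53% | about 0 | 0.13 |
| Own patients only, trial-wide blocks, 10 sites | 52% | about 0 | 0.07 |
| Within-hospital blocks, 5 sites × 10 | 65% | 16.7% | 0.61 |
| Within-hospital blocks, 10 sites × 5 | 56% | 0 | 0.27 |

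**4. Bias.** Suppose each guess shifts the enrolled patient's expected 48-hour change by ± eta points. With the full tally, the excess of correct guesses over 50 patients is 5 × 1.53 = 7.66. The bias is then 2 × 7.66/25 = 0.61 × eta. The documents give no eta, so the values below are assumptions.

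| Assumed eta | Full tally (0.61) | Own-site view (0.07 to 0.13) |
|---|---|---|
| 10 | 6 points | 0.7 to 1.3 |
| 20 | 12 points | 1.4 to 2.6 |
| 25 | 15 points | 1.8 to 3.3 |
| 49 | 30 points | 3.4 to 6.4 |

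With the printed boundaries, SD 100, design effect 1.12 and 40 evaluable patients, the simulated false-positive rate is 4.3% with no bias, 5.9% at 15 points and 10.8% at 30 points.

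**5. Other schemes, full tally.** Fixed blocks of 4, 6 and 8 give 70.8%, 68.3% and 66.6% correct guesses. Hidden random blocks of 4/6/8 remove certainty but raise the guess rate to 67.7%. A big-stick rule (fair coin until the arms differ by 3, then the lagging arm) gives 58% and a bias of 0.32 × eta. It still forces 7.9 of 50 assignments.

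**The case against.** Three objections have weight.

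**The two weaknesses do not meet at an ordinary site.** Block ends fall on the looks at 10, 20 and 30 only if blocks are trial-wide. On that reading a site seeing its own patients guesses barely better than chance. If blocks run within hospital, local staff can predict, but block ends no longer mark the looks, and a site with about 5 patients never completes a block. This stands. A reader might infer that every site can predict assignments from the printed looks; the documents do not support that.

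**Access by the lead hospital is an inference.** A reader might also infer that its enrolling clinicians see the list or all assignments. The SAP says only that the institution performs randomisation, automated in REDCap. This stands as a limit on the claim, but the silence and the conflict with the Protocol are themselves gaps to close.

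**The bias is assumed and small beside the design effect.** At eta of 10 to 20 even the full-tally bias is 6 to 12 points against about 104. SAP 3.2 also declines a rigid cutoff and promises effect sizes with intervals. This largely stands. However, the amendment in SAP 3.1 can change the regimen on a 20% improvement, about 30 points on 149. If that trigger is read between arms, which the text does not say, 15 points is half of it.

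A block of 10 is also less predictable than 4, 6 or 8, so its length is not a poor choice in itself. The difficulty is that it is fixed, published and used without stated access limits.

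**Conclusion.** The weakness is real and worth correcting, but limited. For someone with the full tally of a 5:5 block, 65% of assignments can be guessed and 1.67 of 10 are certain. Who that is depends on facts the documents omit: lead-site or coordinating staff if blocks are trial-wide, or local staff at a site with about 10 patients if blocks are within hospital. For an ordinary site under trial-wide blocks, the reading SAP 3.1 favours, the rate is about 52-53%.

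The bias is 0.61 × eta in the first two cases and about 0.1 × eta in the last. It rests on an assumed eta and on staff acting on every guess, and is probably modest. The documents do not show that selection has occurred or that the primary comparison is compromised. They do leave a route to selection that the planned weighting cannot repair.

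**What to change.** For patients not yet randomised:

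1. Remove the block length from the Protocol's Design section and from the site-facing SAP.
2. Because 10 is already known, generate the remaining list by an undisclosed scheme held in a restricted randomisation file. Balance it within each stage, since the active regimen changes between stages. The balance should be close rather than exact: forced equality at a printed look would again make the last assignment certain to anyone with the tally.
3. Do not default to small blocks of 4/6/8, which raise the full-tally guess rate to 68%.
4. State in both documents the level at which blocks run. Also state that non-enrolling Data Coordinating Center staff generate and hold the list, and that no enrolling staff can see it or the trial-wide running tally.

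The cost is one regenerated REDCap table, a few edited sentences and possibly slight imbalance at a look.

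The big-stick rule is an option, not a required correction. It lowers the guess rate to 58%. Run as one study-wide list, it leaves an imbalance of 4 or more in about 15% of simulations for patients 21-30 and about 21% for patients 21-50.

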### 3.2. Sample size

We anticipate that each of the five centers will enroll 8-12 patients. Sample size and power Analysis was conducted using Pass, vs 14.0 (NCSS, LLC, Kaysville, Utah, USA) and focused on the primary outcome as defined above.

Sample size assumptions:

- power=80%, confidence=95%, and 4 sequential tests(3 interim+1 final), using the Pocock spending function to determine test boundaries,
- potential improvement assumptions based on a previous study 40 with appropriate(e.g., Denver) altitude correction as well as mean baseline PaO2/FiO2=149 with an overestimated standard deviation of 100,
- design effect=1.12 due to the study's multicenter nature (intra-class correlation coefficient=0.03, average cluster=5);
- ~20% inflation to account for premature death

---

 Urbaniak, G. C., & Plous, S. (2013). Research Randomizer (Version 4.0) [Computer software]. Retrieved on April 10, 2020, at <http://www.randomizer.org/>

A sample size of 50 (25 in each intervention group and 25 in the control group) patients detects a >70% improvement in PaO2/FiO2 between intervention groups (both tPA50 and tPA 50 plus drip) and controls, and >91% improvement in PaO2/FiO2 between intervention tPA 50 plus drip) and controls. Recruitment will assume at least 30% increase to account for refusal or inability to consent.

**Consent: We anticipate consenting enough patients to result in 50 eligible patients, thus we plan on a max of 60, to be re-evaluated during each of the interim analyses. LAR, as defined by the state and institutions legislation/policies, will be able to consent.**

The table below shows the details of the interim analyses with the Pocock spending method:

Look	N of Patients	Lower Bndry	Upper Bndry	Nominal Alpha	Inc Alpha	Total Alpha	Inc Power	Total Power
1	10	-2.43798	2.43798	0.015	0.015	0.015	0.18976	0.190
2	20	-2.42677	2.42677	0.015	0.011	0.026	0.25179	0.442
3	30	-2.41014	2.41014	0.016	0.009	0.035	0.21191	0.653
4	50	-2.39658	2.39658	0.017	0.008	0.043	0.14655	0.800

It should be noted that using the traditional (yet arbitrary) confidence level of 95% (alpha=0.05) is not adequate in the current circumstances. The rigid cutoff around what we believe to be a 95% level of certainty, as eloquently put it by Nuzzo in one of the most cited Nature articles, is inappropriate. Thus, for all comparisons, we will present the effect size with appropriate confidence intervals depicting the uncertainty surrounding our estimation. The clinical experience of the investigators working together with the independent DSMB will produce the appropriate interpretation of the results, which can then inform current medical decisions and the next Phase III trial.

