- 2) If at the end of the second intervention deployment (total of 20 patients randomized), the primary outcome improves (PaO₂/FiO₂ ratio at 48 hours) by $\geq 20\%$, or the secondary outcomes PaO₂/FiO₂ ratio at 24 hours improves $\geq 20\%$, or dead space decreases by 15%, or ICU- or ventilator-free days continue to exhibit a positive response (at least 2 days difference), we will modify the mode of administration of the second dose of tPA as follows: following the 50mg tPA bolus, we will initiate a drip of 2 mg/hr tPA over the ensuing 24 hours (total 48 mg infusion) accompanied by an infusion of 500 U/hour heparin during the tPA drip. After this, heparin dose will be increased slowly to maintain a PTT between 60 and 80 sec, titrated per attending's discretion. Interim analyses will be conducted as planned above, and submitted expeditiously to the DSMB, IRB and FDA for approval, yet enrollment will continue while these agencies deliberate and their feedback is received.

See above for the rationale for the tPA50+drip.

Statistical analysis (see attached Statistical Analysis Plan):

All analyses will be conducted initially as an intent-to-treat (patients are analyzed in the group they were randomized to), followed by an as-treated analysis. We will use linear mixed models (continuous outcomes, appropriate transformations if residuals normality departure is detected) or generalized estimating equations (categorical outcomes) to account for intra-hospital cluster effects and repeated measures, with FINAL (OVERALL) significance at $p < 0.05$ (two-tailed tests). If the groups are not comparable, we will compare relative (as opposed to absolute improvement over baseline (with patients as their own controls) to minimize the effect of baseline disparities. In addition, as the sample permits, we will adjust for confounders using a single propensity score adjustor in an inverse probability weighting approach. In addition, we will compare the "dose" of the intervention (i.e., how much of the treatment the patient received) as the effect of interest. The pre-planned final comparisons include within group (improvement over baseline) and between groups, all two-tailed with significance declared according to the alpha defined above by the Pocock spending method.

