## Section 4: Statistical Principles

**4.1. Level of statistical significance:** see above description of p-value for interim analyses.

**4.2. Description and rationale for any adjustment for multiplicity of time points:** There will be no adjustment for multiple outcomes, as all were pre-planned. The investigator-statistician in charge ([name]) strongly agrees with the argument that adjustment for multiple comparisons in pre-planned hypotheses leads to more type II errors.

**4.3. Analysis populations:** all analyses, including safety analyses, will be conducted initially as **intention-to-treat** and then **as-treated**.

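### The final row of the SAP's interim-analysis table carries the boundary for 80% of the information, so the design spends about 0.043 to 0.0455 of alpha instead of the stated 0.05

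*SAP*

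**What the plan says.** SAP 3.2 (Sample size) gives the design as "power=80%, confidence=95%, and 4 sequential tests(3 interim+1 final), using the Pocock spending function to determine test boundaries", and adds "20% inflation to account for premature death". The table that follows is introduced with "The table below shows the details of the interim analyses with the Pocock spending method" and reads:

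| Look | N | Boundary (±) | Nominal alpha | Total alpha | Incremental power | Total power |
|---|---|---|---|---|---|---|
| 1 | 10 | 2.43798 | 0.015 | 0.015 | 0.18976 | 0.190 |
| 2 | 20 | 2.42677 | 0.015 | 0.026 | 0.25179 | 0.442 |
| 3 | 30 | 2.41014 | 0.016 | 0.035 | 0.21191 | 0.653 |
| 4 | 50 | 2.39658 | 0.017 | 0.043 | 0.14655 | 0.800 |

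SAP 3.1 confirms that look 4 is the last: patients are randomised to the drip arm "or Control up to the final analysis at n=50". The protocol's Statistical analysis section tests "with FINAL (OVERALL) significance at $p < 0.05$ (two-tailed tests") and has its final comparisons "all two-tailed with significance declared according to the alpha defined above by the Pocock spending method". SAP 4.1 sets no level of its own; it says "see above description of p-value for interim analyses".

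**The concern.** A spending function releases the whole of the overall alpha at the last look, where the information fraction is 1. A four-look plan at 0.05 should therefore end at a total alpha of 0.050. This table ends at 0.043, and neither document says that any alpha is held back.

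The reader is left with a printed final boundary and a stated method that do not agree. Type I error is safe, because the printed boundary is the stricter of the two. What is at stake is some power in a small trial, and a final threshold open to dispute. The timing makes that worse: the first interim analysis is done, SAP 3.1 describes the trial as "Multicenter, pragmatic, randomized, open label, rapidly adaptive, controlled, clinical trial", and the protocol's amendment of 4 November 2020 cites the oxygenation pattern seen so far. A threshold settled after the final data could be questioned.

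**Working it through.** **Inputs.** Overall two-sided alpha 0.05 (protocol, Statistical analysis; SAP 3.2). Four looks, with boundaries and powers as printed (SAP 3.2). Effect 70% of a baseline mean of 149, SD 100, design effect 1.12 and equal allocation (SAP 3.2). Boundaries and powers below come from recursive numerical integration of the group-sequential density.

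**1. Reproduce the alpha column.** Pocock-type spending is a(t) = 0.05 × ln(1 + (e − 1)t).

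- t = 0.2: 0.05 × ln(1.3437) = 0.0148
- t = 0.4: 0.0262
- t = 0.6: 0.0354
- t = 0.8: 0.05 × ln(2.3746) = 0.0432
- t = 1.0: 0.05 × ln(e) = 0.0500

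The printed totals 0.015, 0.026, 0.035 and 0.043 are the first four. Rows 1 to 3 agree with N/50. Row 4 should be at 50/50 = 1 but carries t = 0.8.

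**2. Reproduce the boundaries.** Solving at t = 0.2/0.4/0.6/0.8 gives 2.43798, 2.42681, 2.41019 and 2.39665, against the printed 2.43798, 2.42677, 2.41014 and 2.39658. With t = 1 at the last look, the first three are unchanged and the fourth becomes 2.281: nominal alpha 0.0225, incremental 0.0500 − 0.0354 = 0.0146.

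**3. Reproduce the power column.** The printed look-1 power of 0.18976 implies a mean test statistic of 1.559 at 10 patients. The SAP's own inputs agree: 0.70 × 149/100 × √(10/(4 × 1.12)) = 1.043 × 1.494 = 1.558. Scaling by √(n/10) and applying the printed boundaries:

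| Looks | Incremental power | Total |
|---|---|---|
| 10/20/30/40 | 0.1898, 0.2518, 0.2119, 0.1466 | 0.800 |
| 10/20/30/50 | 0.1898, 0.2518, 0.2119, 0.2281 | 0.882 |

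The first line matches every printed row. The look-4 count that returns 0.800 is 39.99.

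**4. Overall alpha of the printed boundaries.**

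| Looks | Alpha by look | Total |
|---|---|---|
| 10/20/30/50 | 0.0148 + 0.0114 + 0.0093 + 0.0100 | 0.0455 |
| 10/20/30/45 | 0.0148 + 0.0114 + 0.0093 + 0.0091 | 0.0445 (from unrounded terms) |
| 10/20/30/40 | 0.0148 + 0.0114 + 0.0093 + 0.0078 | 0.0432 |

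None reaches 0.05.

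**5. Power cost.** At the table's own effect, with information proportional to 10/20/30/50 and an assumed uniform loss of patients at every look:

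| Loss | Final boundary 2.39658 | Final boundary 2.281 | Difference (points) |
|---|---|---|---|
| 0% | 0.882 | 0.900 | 1.8 |
| 10% | 0.844 | 0.865 | 2.1 |
| 20% | 0.795 | 0.821 | 2.6 |
| 30% | 0.736 | 0.765 | 2.9–3.0 |

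With 10/20/30/40 evaluable and all four boundaries recomputed to spend 0.05 (2.368, 2.368, 2.358, 2.350), power is 0.814 against 0.800, a cost of 1.4 points.

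**The case against.** The best defence is that the table was built on 40 evaluable patients and that row 4 shows the count after inflation for death: 40/(1 − 0.2) = 50. This explains the power column completely, so the early-look powers are not a second error. It does not rescue the alpha column. If 40 evaluable patients are all the information there is, t is 1 at 40, the looks fall at 0.25/0.5/0.75/1, and the printed boundaries still spend only 0.0432. Rows 1 to 3 would also be evaluable counts sitting beside a randomised count in row 4.

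A second defence is that 0.05 is a ceiling, which 0.0455 and 0.0432 respect, and that only one final boundary is printed. It is true that no false claim can follow. SAP 3.2 also plays down rigid cutoffs and promises effect sizes with confidence intervals, which softens the consequence. Yet SAP 6.4 declares significance by the Pocock spending method, and that method at 0.05 does not give the printed boundary.

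Three cautions stand:

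- The replacement value depends on the information scale. With 40 evaluable and rows 1 to 3 kept, the final boundary is ±2.225; keeping only look 1 and following the function from there, it is about ±2.344.
- Loosening the final boundary after look 1 of an open-label trial invites challenge. Keeping the printed value and declaring the lower alpha does not.
- SAP 3.3 also requires a secondary outcome before stopping early for efficacy. The alphas above are properties of the primary-outcome boundaries; the fuller rule can only lower them.

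**Conclusion.** The concern holds. Row 4 is labelled as the final look at N=50 but carries the values for information fraction 0.8, and the table falls short of the stated 0.05 on every information scale computed: 0.0455 at 10/20/30/50, 0.0432 at 10/20/30/40. On the labelled N the final boundary is ±2.39658 (nominal 0.0165) where full spending gives ±2.281 (nominal 0.0225).

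The error is conservative, at a cost of 1.4 to 3.0 points of power in the scenarios above. It should be fixed because the final threshold is unsettled, not because type I error is at risk. The mismatch in row 4 is certain. Which information scale the sponsor intended is not, since the SAP does not say whether N counts randomised or evaluable patients. These figures concern the repeated looks only, not the unadjusted outcomes or the changes of arm.

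**What to change.** File a new SAP version before the next look or the final analysis. It should define N as randomised or evaluable, add a column of information fractions with t = 1 at the last look, and recompute the power columns on that basis. Then take one of these routes:

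- **Correct row 4 on the labelled N.** Keep rows 1 to 3 and set row 4 to ±2.281, nominal 0.0225, incremental 0.0146, total 0.050.
- **Use another information scale**, if the sponsor can document that it was intended from the start. Keep the boundaries already used and spend only the remaining alpha by the same function.
- **Keep ±2.39658** and state that the overall alpha is 0.0455 (0.043 on equal spacing), not 0.05.

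The third route is the least exposed to a charge of loosening the test after seeing data. Whichever is chosen, the SAP should record that the choice was made without reference to interim results.

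The cost is one definition, one column, one table row or one sentence, and the recomputed powers. No patients are added and no boundary already used changes.
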